## **9.2 Visit 1**

Visit 1 will be Day 1 of the study and will be the day that the subject starts the study drug. If Screening assessments were completed the day before then the subject's physical examination and blood work results can be used for Visit 1 as well. A physical examination including height at 1st visit, weight, vital signs, blood pressure and neurological exam will be performed on the subject. Karnofsky performance status will be assessed. Blood work will be performed for a complete blood count (CBC; RBC count, hemoglobin, hematocrit, absolute reticulocyte count, white blood cell count, absolute neutrophil count, and platelet count), serum chemistry panel for hepatic and renal function (blood urea nitrogen, creatinine, bilirubin [total and direct], aspartate aminotransferase [AST], and alanine aminotransferase [ALT]). If the subject is a female, then menstrual status will be assessed and a serum pregnancy test will also be performed. Blood for pharmacodynamic marker analysis will be collected, if applicable (Appendix J). All concomitant therapies will be documented. The subject will be dispensed a 21-day supply of the study drug once all evaluable criteria are met and will start the study drug on Day 1. Visit 1 should occur within 7 days following a blood transfusion.

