#### **9.5 Visit 4**

Visit 4 will be Day 29 ( $\pm 2$  days) of the study (Follow-up Period). The subject will undergo post-treatment safety assessment including a physical examination and blood work (CBC and chemistry panel). Transfusion history will be documented. The subject will be questioned and evaluated for any adverse events. This visit may be done virtually through a system that can visually assess the subject for neurologic issues. Blood work may be done at a local laboratory.

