In the present study, TFP will be investigated in subjects with DBA over a lower dose range than is generally employed in subjects with schizophrenia. The maximum anticipated daily dose will be 10 mg. In contrast, the usual initial adult dose of TFP for schizophrenia is 2 to 5 mg orally 2 times a day with a maintenance dose of 15 to 20 mg/day and a maximum dose of 40 mg/day. Therefore, more severe adverse reactions with TFP may be less likely to occur in the current study.

The only alternative to this treatment is not to participate in this trial. The subject will continue on transfusion therapy during this trial and be transfused every 3-4 weeks when the hemoglobin is less than 8 gm/dL as prior.

Given the serious potential side effects of chronic, often life-long transfusion therapy and the continuous need for chelation therapy, the risks of this short, 3-week study (plus 1 week follow-up) are reasonable for this subject population. The preliminary data from the zebrafish and mice models and information gained from this study will be proof-of-principle of the use of this drug in the treatment of DBA. If no significant toxicity to this drug is noted, the drug will be chemically altered as to not cross the blood-brain barrier and potentially be a viable treatment for DBA, without the untoward neurological side effects.

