## **15.4 Stopping Rules**

The stopping rules are as follows:

Scenario 1: The occurrence of extrapyramidal symptoms, symptoms suggestive of tardive dyskinesia (including vermicular movements of the tongue), neuroleptic malignant syndrome or any SAE or treatment-emergent AE  $\geq$  Grade 3 felt to be causally related to TFP in a single subject:

- Rule: Treatment will be immediately stopped in that subject and the subject will be discontinued from the study.

Scenario 2: The occurrence of the extrapyramidal symptoms, symptoms suggestive of tardive dyskinesia (including vermicular movements of the tongue), neuroleptic malignant syndrome or the same SAE or treatment-emergent AE  $\geq$  Grade 3 felt to be causally related to TFP in more than 1 subject:

- Rules:
  - a. Treatment will be immediately stopped in those subjects and those subjects will be discontinued from the study.
  - b. If the 2 or more subjects are in Cohort A, the trial will be stopped; no MTD will be declared.
  - c. If the 2 or more subjects are in Cohort B, the study will be stopped, and 1 mg/day will be declared the MTD.

- d. If the 2 or more subjects are in Cohort C, the study will be stopped, and 2 mg/day will be declared the MTD.
- e. If the 2 or more subjects are in Cohort D, the study will be stopped, and 5 mg/day will be declared the MTD.

Scenario 3: Hemoglobin > 12 mg/dL in a subject sustained for more than 7 days (not associated with RBC transfusion)

- Rule: The subject will be considered a complete responder, treatment will be discontinued, and the duration of the effect will be monitored until day 29 after start of treatment.

In addition to the stopping rules, a subject may be discontinued by the investigator at any time for failure to comply with protocol requirements, in the event that the investigator feels that continuation in the study poses a risk to the health of the subject, or if the subject withdraws consent.

The reason for treatment discontinuation must be documented in the subject chart / source records.

The trial will be stopped, as noted above, if more than one subject experiences the occurrence of the extrapyramidal symptoms, symptoms suggestive of tardive dyskinesia, neuroleptic malignant syndrome, the same SAE or treatment-emergent AE  $\geq$  Grade 3 felt to be causally related to TFP at the lowest dose level.

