## 22.1 Appendix A continued

\*Historical clinical laboratory evaluations performed for medical evaluation within 28 days are acceptable for study entry.

- a: All Day 1 assessments are to be done prior to TFP administration. TFP should be initiated within 7 days following a blood transfusion.
- b: Hematology laboratory evaluations (RBC count, hemoglobin, hematocrit, absolute reticulocyte count, white blood cell count, absolute neutrophil count, and platelet count) will be collected at Screening and at subsequent visits during the Treatment and Follow-Up Periods, as referenced in the schedule above. Any laboratory evaluations may be repeated more frequently if clinically indicated.
- c: Serum chemistry laboratory evaluations (blood urea nitrogen, creatinine, bilirubin [total and direct], aspartate aminotransferase [AST], alanine aminotransferase [ALT]) will be collected at Screening and at subsequent visits during the Treatment and Follow-Up Periods, as referenced in the schedule above. Any laboratory evaluations may be repeated more frequently if clinically indicated.
- d: Blood for pharmacodynamic disease marker analysis will be shipped to supporting company (see Appendix F).
- e: Females of childbearing potential: A female of childbearing potential is a sexually mature woman who has not undergone a hysterectomy or who has not been postmenopausal for at least 24 consecutive months (i.e., who has had menses at some time in the preceding 24 months). A serum pregnancy test (which must be negative) must be performed not more than 3 days from the start of TFP administration (Study Day 1). Subjects must agree to use highly effective methods of birth control during study participation and for at least 1 week following the last dose of TFP. Subjects must be counseled concerning measures to be used to prevent pregnancy and potential toxicities prior to the first dose of TFP. Serum pregnancy tests will be performed according to the above schedule during study participation.
- f: Subjects must have documented transfusion history for > 12 weeks before inclusion/initiation of treatment.

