#### **Description of procedure**

The study is 29 days long and consists of taking the study drug TFP for 21 days and being monitored for an additional 8 days. The patient will have a total of 4 visits over the period of 29 days. A review of the patient's history, physical examination, and laboratory blood work will be

done in order to determine if the patient is eligible to participate. While the patient is taking the TFP, he or she will need to be seen at The Feinstein Institutes for Medical Research or the participating institution 3 times over the first 21 days and virtually for the last visit. During the first 21 days the patient will be taking TFP once a day, orally as a tablet, and will continue the red blood cell transfusions as routinely scheduled, every 3-4 weeks.

The following are some of the basic inclusion and exclusion criteria for this pilot trial.

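### The complete-responder label in Stopping Rules Scenario 3 cannot be applied reliably: transfusion association is undefined, and the visit days hardly allow the more-than-7-day test

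*Combined protocol and SAP*

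**What the plan says.** **The rule.** Section 15.4, Scenario 3, applies to hemoglobin above 12 (unit printed as mg/dL) "in a subject sustained for more than 7 days (not associated with RBC transfusion"). Its consequence is: "The subject will be considered a complete responder, treatment will be discontinued, and the duration of the effect will be monitored until day 29".

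**Transfusion before dosing.** Section 9.2 states: "Visit 1 should occur within 7 days following a blood transfusion". Note a to Appendix A repeats this: "TFP should be initiated within 7 days following a blood transfusion".

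**Transfusion during the study.** Section 10 says that subjects will "be transfused every 3-4 weeks when the hemoglobin is less than 8 gm/dL as prior". The study announcement (Appendix G, description of procedure) gives no hemoglobin condition: the patient "will continue the red blood cell transfusions as routinely scheduled, every 3-4 weeks".

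**Readings.** Sections 9.3 to 9.5 and Appendix A schedule post-baseline hemoglobin at Visit 2 (Day 11 ±1), Visit 3 (Day 22 ±2) and Visit 4 (Day 29 ±2). Dosing lasts at most 21 days (Sections 6.1 and 8.2). Notes b and c to Appendix A allow extra laboratory tests if clinically indicated, but no confirmatory hemoglobin is required. Absolute reticulocyte count is part of the hematology panel at every visit. Transfusions are recorded too; at Visit 4, for example, "Transfusion history will be documented".

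**Analysis.** Sections 6.2 to 6.4 list safety and pharmacodynamic markers as endpoints. Section 14.2 summarizes adverse events and laboratory grades and marks secondary endpoints as not applicable. No response analysis is planned.

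**The concern.** Scenario 3 is the only place where the protocol defines a response, and it has two conditions that the rest of the design does not support.

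First, a value must not be associated with transfusion, in a population where everyone has just been transfused. No passage gives a number of days, a comparison with the subject's usual decline, or any other test. The related wording in Sections 3.5.2, 6.1 and 7.6.1 is equally undefined.

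Second, persistence for more than 7 days must be shown from three post-baseline readings, of which only the first falls inside dosing on the nominal days.

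The study is open-label, uncontrolled and has at most 24 subjects. Section 2 says that, if the drug is tolerated, the trial will support a proof-of-concept trial or a modified drug, and Section 10 speaks of proof-of-principle. One reported complete responder, or none, could be read as information on activity when it reflects visit dates and individual judgment.

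**Working it through.** **The plan's own figure.** The only design figure is the sample size: one cohort of 3 gives the minimum of 3, and 4 cohorts × 6 = 24 gives the maximum. Both reproduce. Neither enters this point.

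**Inputs.** Day 1 is the first dose and Day 21 the last. Visit windows are V2 = Days 10–12, V3 = Days 20–24 and V4 = Days 27–31. The index transfusion is 0–7 days before Day 1, and the repeat interval is 21–28 days.

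**Step 1: time since the index transfusion** = (visit day − 1) + (0 to 7).

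| Visit | Nominal | With windows |
|---|---|---|
| V1 | 0–7 | 0–7 |
| V2 | 10–17 | 9–18 |
| V3 | 21–28 | 19–30 |
| V4 | 28–35 | 26–37 |

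**Step 2: next transfusion.** Study day = 1 + (21 to 28) − (0 to 7) = Day 15 to Day 29.
- *Routine repeats (Appendix G).* Every reading is at most 27 days after the latest transfusion. A new transfusion falls on or before V3 in 37 of 40 combinations of visit day and index day on a 21-day cycle, and in 6 of 40 on a 28-day cycle.
- *Only when hemoglobin is below 8 (Section 10).* A subject with sustained high hemoglobin is not re-transfused, so V3 can be 30 days and V4 37 days after transfusion.

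The two statements therefore give different transfusion exposure at the confirming visit. Under neither is it stated which values count.

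**Step 3: gaps between post-baseline readings.**
- V2 to V3: 22 − 11 = 11 days nominally; range 20 − 12 = 8 to 24 − 10 = 14. More than 7 days in 15 of 15 combinations.
- V3 to V4: 29 − 22 = 7 days nominally, which is not more than 7; range 27 − 24 = 3 to 31 − 20 = 11. For V3 on Days 20, 21, 22, 23 and 24, the number of V4 days more than 7 days later is 4 + 3 + 2 + 1 + 0 = 10 of 25.

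These are counts of permitted combinations, not probabilities.

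**Step 4: position relative to dosing.** The V2–V3 pair is completed nominally on Day 22, one day after the last dose. V3 falls within dosing only on Day 20 or 21 (2 of 5 window days), with at most one dose left. Sections 2 and 7.5 mention weekly monitoring or visits, which the schedule does not provide. Even weekly visits on Days 8, 15 and 22 would not help, because the two on-drug readings are 15 − 8 = 7 days apart.

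**Step 5: duration of effect.** For a subject who qualifies at Day 22, only the Day 29 reading remains scheduled.

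**Step 6: could transfusion alone produce the label?** The documents give no rise per unit, so a range of 0.75–2 g/dL is assumed. Section 7.1 describes 2 units per 28 days; both are assumed to be given together.
- From 8 g/dL: 8 + 2 × 0.75 = 9.5, up to 8 + 2 × 2 = 12.0. Never above 12.
- From 9 g/dL: 9 + 2 × 1.5 = 12.0; 9 + 2 × 2 = 13. Above 12 only at the extreme, and the value would still have to persist for more than 7 days.

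**The case against.** The strongest reply is that this is a safety study. Response is not an objective, an endpoint or an analysis, and the label is one line in a stopping rule. Section 2 makes the next step depend on tolerability and places proof of concept in a separate study. All of this stands, and it limits the importance of the point. It does not make the rule workable.

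Some stronger inferences are tempting, but the documents do not support them:
- *That no subject could ever qualify.* This would require hemoglobin free of donor cells, a test stated nowhere. A subject above 12 on Days 11 and 22 without a new transfusion could reasonably be judged a responder.
- *That every scheduled value lies within 28 days of a transfusion.* This holds under the announcement's routine schedule but fails under Section 10's condition.
- *That persistence can be tested only after dosing ends.* This is true on nominal days, but Visit 3 may fall on Day 20 or 21, and unscheduled tests are allowed.
- *That transfusion alone would create false responders.* Step 6 does not show this, and Scenario 3 excludes transfusion-associated values in any case.

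It can also be said that the stopping action does not need the 7-day test, because Section 6.1 discontinues treatment above 12 with no duration stated. That is correct, but it exposes a conflict: a subject above 12 on Day 11 would stop under Section 6.1 before Scenario 3 could be assessed.

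**Conclusion.** The point holds in limited form. Scenario 3 states a response criterion that its own schedule cannot apply reliably. Transfusion association is undefined for subjects who all start within 7 days of a transfusion. On nominal days the first qualifying pair is complete one day after the last dose. A rise first seen at Visit 3 passes or fails by visit date (10 of 25 combinations, and not on the nominal days). Classification is therefore arbitrary or likely to miss a response.

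This rests on the scheduled readings alone, with Day 21 as the last dose; unscheduled tests would soften the timing problem but would not settle attribution. A reader might infer that the dose-finding result is compromised. It is not: neither the MTD nor the primary safety analysis uses the label. The change should be made, but the trial's main conclusion does not depend on it.

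**What to change.** 1. Remove the complete-responder label from Scenario 3. If it is kept, state beforehand the transfusion-free interval that a hemoglobin value needs in order to count and the readings that establish persistence, and report not evaluable otherwise. The sponsor must set that interval; none is proposed here.
2. Describe by dose the change in absolute reticulocyte count from Day 1 at Days 11, 22 and 29, beside each subject's recorded on-study transfusions. Reticulocytopenia is one of the diagnostic criteria in Appendix B, and the count is already scheduled at every visit. Keep this descriptive. A comparison of pre-transfusion hemoglobin with the prior 12 weeks is not suggested, because the documents require transfusion history for that period but not historical hemoglobin.
3. Reconcile the hemoglobin-triggered discontinuation passages with each other and with the visit schedule: Section 3.5.2 (sustained rise of at least 2 g/dL), its guidelines table (at least 12 g/dL), Section 6.1 (above 12 g/dL, no duration), Section 7.6.1 (sustained, at least 12, printed as mg/dL) and Section 15.4 (above 12, printed as mg/dL, for more than 7 days). Reconcile the transfusion wording in Section 10 with Appendix G. Which rule is right is for the sponsor to decide.

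The cost is protocol wording and one descriptive table from scheduled data. The trial gives up a label that it cannot support.

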### **15.5 Medical Monitoring**

It is the responsibility of the Principal Investigator to oversee the safety of the study at his/her site. This safety monitoring will include careful assessment and appropriate reporting of adverse events as noted above, as well as the construction and implementation of a site data and safety monitoring plan (see [Section 17 Auditing, Monitoring and Inspecting](#)). Medical monitoring will include a regular assessment of the number and type of SAEs.

### **15.6 Data and Safety Monitoring**

The medical monitor will serve as the monitoring entity for this study. The monitor will be a qualified physician, other than the Principal Investigator, who is not associated with the protocol, and will monitor the study to protect the safety and well-being of the subjects. The medical monitor plays a role in reviewing serious adverse events and unanticipated problems.

The physician will not be involved with the conduct of the study, but will serve as a hematology consultant.

For this study [name] has been selected as the Medical Monitor. He has served in this role in a prior DBA clinical study. He is the Deputy Chief, Operations and Safety, in the Division of Hematology/Oncology and Stem Cell Transplantation at Cohen Children's Medical Center and as such meets the criteria stated above.

Summary data related to the study will be provided to the medical monitor in written form. The following materials will be provided: a report of all deaths, a summary of cumulative adverse event data with intervention causality, a summary of assessment of conduct of the study (e.g. site enrollment, subject enrollment (target vs. actual), protocol compliance per site, informed consent records, treatment received), and a summary of assessment to evaluate factors that may impact on the safety of study subjects.

Adverse Event (AE) Data: The frequencies of each type of AE will be tabulated and the incidence rate will be computed as the percentage of subjects experiencing that AE at some time during the course of the trial. These intervals will be used by the medical monitor for determining whether a particular AE or class of AEs should be "flagged" for safety concerns.

Severe AE/Major Protocol Deviation: Should any major or serious adverse event or protocol deviation occur that requires rapid action, the Sponsor-Investigator will notify the IRB, and FDA by telephone, and in writing within 24 hours.

Meeting Schedule: The medical monitor will review the data quarterly, or as necessary for major infractions of protocol or SAEs. Meetings may be by telephone.

Reports from the Medical Monitor: After the Medical Monitor meets, a written summary of the meeting will be provided to the Sponsor-Investigator. The summary will include:

- Date that the meeting took place
- Summary of cumulative adverse event data
- Recommendations

Distribution of Report: The Sponsor-Investigator will distribute the report to the Northwell IRB and all co-investigators, and the FDA.

## **16 Data Handling and Record Keeping**

### ***16.1 Confidentiality***

Information about study subjects will be kept confidential and managed according to the requirements of the Health Insurance Portability and Accountability Act of 1996 (HIPAA). Those regulations require a signed subject authorization informing the subject of the following:

- What protected health information (PHI) will be collected from subjects in this study
- Who will have access to that information and why

- Who will use or disclose that information
- The rights of a research subject to revoke their authorization for use of their PHI.

In the event that a subject revokes authorization to collect or use PHI, the investigator, by regulation, retains the ability to use all information collected prior to the revocation of subject authorization. For subjects that have revoked authorization to collect or use PHI, attempts should be made to obtain permission to collect at least vital status (i.e. that the subject is alive) at the end of their scheduled study period.

## **16.2 Source Documents**

Source data is all information, original records of clinical findings, observations, or other activities in a clinical trial necessary for the reconstruction and evaluation of the trial. Source data are contained in source documents. Examples of these original documents, and data records include: hospital records, clinical and office charts, laboratory notes, memoranda, subjects' diaries or evaluation checklists, pharmacy dispensing records, recorded data from automated instruments, copies or transcriptions certified after verification as being accurate and complete, microfiches, photographic negatives, microfilm or magnetic media, x-rays, subject files, and records kept at the pharmacy, at the laboratories, and at medico-technical departments involved in the clinical trial.

## **16.3 Case Report Forms**

The study case report form (CRF) is the primary data collection instrument for the study. All data requested on the CRF must be recorded. All missing data must be explained. If a space on the CRF is left blank because the procedure was not done or the question was not asked, write "N/D". If the item is not applicable to the individual case, write "N/A". All entries should be printed legibly in black ink. If any entry error has been made, to correct such an error, draw a single straight line through the incorrect entry and enter the correct data above it. All such changes must be initialed and dated. DO NOT ERASE OR WHITE OUT ERRORS. For clarification of illegible or uncertain entries, print the clarification above the item, then initial and date it.

## **16.4 Records Retention**

It is the Investigator's responsibility to retain study essential documents for at least 2 years after the last approval of a marketing application in their country and until there are no pending or contemplated marketing applications in their country or at least 2 years have elapsed since the formal discontinuation of clinical development of the investigational product. These documents should be retained for a longer period if required by an agreement with the sponsor. In such an instance, it is the responsibility of the sponsor to inform the investigator/institution as to when these documents no longer need to be retained.

